8.0 Study Drug Exposure and Compliance

8.1 Study Drug Exposure

The duration of exposure to study drug will be summarized for the safety analysis set by the randomized treatment groups (placebo group vs Upadacitinib 15 mg QD) in Period 1. For long term, the duration of exposure to study drug will be summarized for the safety analysis set only for the Any Upadacitinib 15 mg QD group, which includes Upadacitinib

15 mg QD exposure from subjects starting on Upadacitinib 15 mg QD and subjects switching from placebo to Upadacitinib 15 mg QD.

Exposure to upadacitinib and placebo is defined as last dose date minus first dose date plus 1 day.

The duration of exposure to study drug will be summarized for each group as specified above, with the number of subjects, mean, standard deviation, median, minimum and maximum values. In addition, the number and percentage of subjects exposed to study drug will be summarized for the following cumulative duration intervals.

- ≥ 2 weeks
- ≥ 1 month
- ≥ 3 months
- ≥ 6 months
- ≥ 9 months
- ≥ 12 months
- ≥ 18 months
- ≥ 2 years

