10.2.2 Analysis of Long-Term Adverse Event

Long-term adverse events will be analyzed using event rates adjusted by cumulative exposure and will be based on the actual treatment received at the time of AE occurrence. According to the study design, randomized placebo subjects switch to Upadacitinib 15 mg

QD when entering Period 2, this analysis will be reported for Any Upadacitinib 15 mg QD subjects. The Any Upadacitinib 15 mg QD treatment group is defined as subjects who receive at least one dose of Upadacitinib 15 mg QD at any time during the study.

This includes AEs occurred under Upadacitinib 15 mg QD exposure from subjects starting on Upadacitinib 15 mg QD and subjects switching from placebo to Upadacitinib 15 mg QD.

Exposure-Adjusted Event Rate (EAER)

To adjust for potentially different follow-up time between treatment groups, EAER will be provided. For the purpose of event rate calculation, the numerator will be the total number of AEs reported for the event (i.e., a subject can contribute more than one event to the numerator) and the denominator will be the total exposure time among subjects under the treatment group. The number of AEs reported (numerator), the total number of years of study drug exposure (denominator), and the exposure-adjusted AE event rate per 100 patient-years calculated as $([\text{numerator (days)}/\text{denominator}])/365.25 \cdot 100$ will be presented for each treatment group. The EAER will be the main approach to evaluate AEs in the long-term analysis.

In addition, the exposure-adjusted incidence rate (censored at first event) will be conducted for AESI endpoints as deemed appropriate for long-term analysis.

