10.2.2.1 Overview of Adverse Events Rates per 100 Patient-Years of Study Drug Exposure

An overview of AEs per 100 patient-years of study exposure will be presented for Any Upadacitinib 15 mg QD for the following AE categories.

- All TEAEs
- Treatment-emergent serious adverse events (SAEs)
- Treatment-emergent severe adverse events
- TEAEs reasonably possibly related to study drug
- TEAEs of special interest

- TEAEs leading to discontinuation of study drug
- TEAE leading to death

The number of TEAEs reported, the total number of years of study drug exposure, and the TEAE rate per 100 patient-years will be presented for Any Upadacitinib 15 mg QD group.

Additional AEs may be considered for tabulation/summary based on recommendations from Clinical and Safety as deemed appropriate.

For TEAE of special interest, the point estimate and 95% CI (using normal approximation) will be provided for the Any Upadacitinib 15 mg QD group in AE rate per 100 patient-years (refer to [Appendix B](#)).

10.2.2.2 Adverse Events Rates per 100 Patient-Years of Study Drug Exposure by SOC and PT

For the Any Upadacitinib 15 mg QD treatment group, the TEAE rate per 100 patient-years of exposure as outlined in Section [10.2.2.1](#) will be calculated overall, for each SOC and each PT, for each of the following events:

- All TEAEs
- Treatment-emergent serious adverse events (SAEs)
- Treatment-emergent severe adverse events
- TEAEs reasonably possibly related to study drug
- TEAEs leading to discontinuation of study drug
- TEAE leading to death

10.2.2.3 Adverse Events of Special Interest Rates per 100 Patient-Years of Study Drug Exposure

The Adverse Events of Special Interest (AESI) categories will be summarized and presented for the Any Upadacitinib 15 mg QD treatment group using SOC and MedDRA PT (for adjudicated cardiovascular events, the CAC adjudicated categories will be used).

The AESI categories will be identified per Standard MedDRA Queries (SMQs)/Company MedDRA Queries (CMQs).

The Adverse Events of Special Interest (AESI) rate per 100 patient-years of exposure as outlined in Section 10.2.2.1 will be calculated overall, for each SOC and each PT, for each of the AESI listed in Section 10.2.1.6.

10.2.2.4 Listing of Serious Adverse Events (Including Deaths) and Adverse Events Leading to Study Drug Discontinuation

All serious adverse events (SAEs), deaths, and adverse events leading to discontinuation of study drug will be listed.

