Appendix B. EAER and Normal Approximation Based 95% Confidence Interval

Assume the occurrence of TEAE of special interest follows a Poisson distribution and let λ denote the rate of occurrence of TEAE under the total exposure time for a treatment group. Let n be the number of AEs reported in Any Upadacitinib 15 mg QD group. Let T be the total number of days exposed to study drug summed across all treated subjects in Any upadacitinib 15 mg QD group. Under the assumption that n follow Poisson distribution with parameters λT , the $\hat{\lambda} = n/T$.

Using normal approximation, the 95% confidence interval can be calculated by (Liu GF, et al. 2006.):

$$\hat{\lambda} \pm Z_{\alpha/2} \hat{\sigma}$$

Where $\hat{\sigma} = \sqrt{\frac{n}{T^2}}$

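### The SAP formula for the long-term exposure-adjusted adverse event rate divides by 365.25 although exposure is in years, and Appendix B does not state the conversion of its per-day interval

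*SAP*

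**What the plan says.** SAP Section 10.2.2 defines the exposure-adjusted event rate (EAER) for the pooled Any Upadacitinib 15 mg QD group and gives it a central role: "The EAER will be the main approach to evaluate AEs in the long-term analysis".

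- **Numerator.** Section 10.2.2: "the numerator will be the total number of AEs reported for the event". A subject may contribute more than one event, so this is a plain count.
- **Denominator and formula.** The same section lists "the total number of years of study drug exposure (denominator), and the exposure-adjusted AE event rate per 100 patient-years calculated as" the numerator, tagged with the unit days, over the denominator, the quotient then divided by 365.25 and multiplied by 100.
- **Reporting.** Section 10.2.2.1 keeps years as the unit: "The number of TEAEs reported, the total number of years of study drug exposure, and the TEAE rate per 100 patient-years will be presented". For AESIs it also asks for a point estimate and 95% CI per 100 patient-years, and refers to Appendix B.
- **Interval.** Appendix B lets T "be the total number of days exposed to study drug summed across all treated subjects". The rate is n/T and its standard error is the square root of n/T². No scaling to 100 patient-years is given.
- **Exposure.** Section 8.1: "Exposure to upadacitinib and placebo is defined as last dose date minus first dose date plus 1 day". The raw quantity is therefore in days.

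**The concern.** An event count divided by years and multiplied by 100 is already a rate per 100 patient-years. A further division by 365.25 has no role, and the days label has no meaning on a count. Appendix B works in days, so the point estimate in Section 10.2.2 and the interval in Appendix B are written on two scales. Neither, followed literally, is the one to be reported.

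The rate is applied to all TEAEs, SAEs, severe and related events, events leading to discontinuation, deaths, each SOC and PT, and each AESI. It is reported for one pooled group, so the absolute value is the result, and a scale error cannot cancel in a comparison of groups within the table.

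**Working it through.** The documents state no numerical rate, so there is no figure to reproduce. The check is of units, followed by one worked example.

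**Units.** Let n be the number of events, Y the exposure in years and D the exposure in days, with Y = D/365.25.

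- Target: n/Y × 100 = n/(D/365.25) × 100 = (n/D) × 36,525.
- As written, with years as the sentence says: (n/Y)/365.25 × 100. Target divided by this = 365.25.
- As written, with days: (n/D)/365.25 × 100. Target divided by this = 365.25² = 133,408 (rounded).

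These ratios do not depend on n or on the amount of exposure.

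**Example (assumed inputs).** Take full exposure for the planned 85 subjects over 104 weeks and 85 over 90 weeks, and suppose 100 events.

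- D = 85 × 728 + 85 × 630 = 61,880 + 53,550 = 115,430 days.
- Y = 115,430/365.25 = 316.03 years.
- Target: 100/316.03 × 100 = 31.64 per 100 patient-years.
- As written, years: (100/316.03)/365.25 × 100 = 0.0866.
- As written, days: (100/115,430)/365.25 × 100 = 0.000237.

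**Appendix B, same inputs.**

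- Rate: 100/115,430 = 0.000866 per day.
- Standard error: √100/115,430 = 0.0000866.
- 95% limits: 0.000697 to 0.001036 per day.
- Multiplied by 36,525: 31.64, with limits 25.44 to 37.84 per 100 patient-years.

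Appendix B thus returns the right answer once the factor of 36,525 is applied. The SAP does not state that factor.

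**Could a misplaced bracket explain it?** Moving only the bracket gives n/(denominator/365.25) × 100. With the denominator in years this is 31.64 × 365.25 = 11,557, now 365.25 times too high. The formula works only if the days label also moves to the denominator, and that contradicts the word years in the same sentence.

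**The case against.** The best defence is that the intent is plain. The words around the formula define a count, years of exposure and a rate per 100 patient-years, and that fixes the quantity as n/Y × 100. The formula contains exactly the pieces of a correct one, n/(D/365.25) × 100, with the label and bracket misplaced. It was read from a PDF by a program, so some of that could be an artefact. The count, the years and the rate are shown together, so 100 events in 316 years beside a rate of 0.09 would probably be noticed.

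Most of this stands, and it lowers the practical risk. It does not make the text right. The bracket alone cannot reconcile years with a 365.25 conversion, no other section gives a corrected formula, and a programmer working from the SAP would have to guess.

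A reader might also draw three stronger conclusions that the documents do not support:

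- **That every long-term safety table is wrong.** Long-term laboratory, liver and vital-sign summaries (Sections 10.3.3 and 10.4.3) use descriptive statistics, or numbers and percentages of subjects.
- **That the Appendix B interval is wrong.** Its estimate and limits share one scale, per day. It lacks only the conversion, which is a constant multiplier.
- **That long-term risks would look negligible.** Event counts and exposure years appear beside the rate, SAEs, deaths and discontinuations are listed individually (Section 10.2.2.4), and an exposure-adjusted incidence rate is added for AESIs.

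**Conclusion.** The formula in SAP Section 10.2.2 is wrong as written. Under its own stated unit, years, every long-term adverse event rate would be 365.25 times too low. The factor of 133,408 arises only if exposure is entered in days, against the wording of the sentence, and should not be quoted as the size of the error. Appendix B is sound within itself but omits the step to the scale that Section 10.2.2.1 requires.

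The factor of 365.25 needs no assumption about events or exposure; only the worked rates do. The one reservation is the exact bracket and label placement, which should be confirmed in the original PDF. This is most likely a drafting error. It does not show that any reported rate is wrong, since the documents do not reveal what was programmed. It does not touch the Week 14 efficacy analyses. It still needs correcting, because it is the stated rule for the main long-term adverse event measure.

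**What to change.** Amend the SAP before the Week 104 lock:

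1. **Section 10.2.2.** Replace the formula with: EAER per 100 patient-years = 100 × (number of TEAEs) / (total exposure in days / 365.25). Remove the days label from the numerator.
2. **Appendix B.** Either define T in patient-years and multiply the estimate and both limits by 100, or keep T in days and multiply all three by 36,525.
3. **Rates already produced.** Section 11.0 records a Week 64 lock completed in February 2020. If exposure-adjusted rates were produced then or later, check the conversion in the program against count / years × 100.

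The cost is a few lines of SAP text and a short program check. No data collection, procedure or other analysis changes.

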10.2.2.1 Overview of Adverse Events Rates per 100 Patient-Years of Study Drug Exposure

An overview of AEs per 100 patient-years of study exposure will be presented for Any Upadacitinib 15 mg QD for the following AE categories.

- All TEAEs
- Treatment-emergent serious adverse events (SAEs)
- Treatment-emergent severe adverse events
- TEAEs reasonably possibly related to study drug
- TEAEs of special interest

- TEAEs leading to discontinuation of study drug
- TEAE leading to death

The number of TEAEs reported, the total number of years of study drug exposure, and the TEAE rate per 100 patient-years will be presented for Any Upadacitinib 15 mg QD group.

Additional AEs may be considered for tabulation/summary based on recommendations from Clinical and Safety as deemed appropriate.

For TEAE of special interest, the point estimate and 95% CI (using normal approximation) will be provided for the Any Upadacitinib 15 mg QD group in AE rate per 100 patient-years (refer to [Appendix B](#)).

10.2.2.2 Adverse Events Rates per 100 Patient-Years of Study Drug Exposure by SOC and PT

For the Any Upadacitinib 15 mg QD treatment group, the TEAE rate per 100 patient-years of exposure as outlined in Section [10.2.2.1](#) will be calculated overall, for each SOC and each PT, for each of the following events:

- All TEAEs
- Treatment-emergent serious adverse events (SAEs)
- Treatment-emergent severe adverse events
- TEAEs reasonably possibly related to study drug
- TEAEs leading to discontinuation of study drug
- TEAE leading to death

10.2.2.3 Adverse Events of Special Interest Rates per 100 Patient-Years of Study Drug Exposure

The Adverse Events of Special Interest (AESI) categories will be summarized and presented for the Any Upadacitinib 15 mg QD treatment group using SOC and MedDRA PT (for adjudicated cardiovascular events, the CAC adjudicated categories will be used).

The AESI categories will be identified per Standard MedDRA Queries (SMQs)/Company MedDRA Queries (CMQs).

The Adverse Events of Special Interest (AESI) rate per 100 patient-years of exposure as outlined in Section 10.2.2.1 will be calculated overall, for each SOC and each PT, for each of the AESI listed in Section 10.2.1.6.

10.2.2.4 Listing of Serious Adverse Events (Including Deaths) and Adverse Events Leading to Study Drug Discontinuation

All serious adverse events (SAEs), deaths, and adverse events leading to discontinuation of study drug will be listed.

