10.2.1.6 Adverse Events of Special Interest

The Adverse Events of Special Interest (AESI) categories will be summarized and presented by treatment groups using SOC and MedDRA PT. The AESI categories will be identified by the following search criteria per Standard MedDRA Queries (SMQs)/Company MedDRA Queries (CMQs) in [Table 9](#) below. Adjudicated

cardiovascular events will be summarized and presented by treatment group using the CAC adjudicated categories.

Table 9. AESI for Upadacitinib with SMQs/CMQs/PTs Searches

AESI	Type of MedDRA Query	Broad or Narrow Search	SMQ/CMQ Search Criteria
Serious Infections	CMQ		"Infections" – Subset for SAEs
Opportunistic Infection excluding Tuberculosis and Herpes Zoster	CMQ		"Opportunistic Infection excluding Tuberculosis and Herpes Zoster"
Possible Malignancy	SMQ	Narrow	"Malignancies"
Malignancy	SMQ	Narrow	"Malignant tumours"
Non-Melanoma Skin Cancer (NMSC)	SMQ	Narrow	Skin Malignant tumours (narrow SMQ) removing Melanoma CMQ
Malignancy excluding NMSC			"Malignant tumours" Narrow SMQ removing NMSC output
Lymphoma	SMQ	Broad	"Malignant Lymphomas"
Hepatic Disorder	SMQ	Narrow	"Drug Related Hepatic Disorders"
Adjudicated Gastrointestinal Perforations	Based on adjudicated results (the identification of events to be adjudicated are described in the GI Perforation charter)		
Anemia	CMQ		"Non-Hemolytic and Non-Aplastic Anemias"
Neutropenia	CMQ		"Hematological Toxicity – Neutropenia"
Lymphopenia	CMQ		"Hematological Toxicity – Lymphopenia (Veliparib Product Specific)"

Table 9. AESI for Upadacitinib with SMQs/CMQs/PTs Searches (Continued)

AESI	Type of MedDRA Query	Broad or Narrow Search	SMQ/CMQ Search Criteria
Herpes Zoster	CMQ		"Herpes Zoster"
Creatine Phosphokinase (CPK) Elevation	PT		Search only for the PT of "Blood creatine phosphokinase increased"
Renal Dysfunction	SMQ	Narrow	"Acute Renal, Failure"
Active Tuberculosis	CMQ		"Active Tuberculosis"
Adjudicated Cardiovascular Events	Output from CAC		
MACE*			
Undetermined/Unknown Cause of Deaths			
Other Cardiovascular events			
Adjudicated Thrombotic Events	Output from CAC		
Venous Thromboembolic Events**			
Other Venous Thrombosis			
Arterial Thromboembolic Events (non-cardiac, non-neurologic)			

* MACE; Major Adverse Cardiovascular Events, defined as cardiovascular death, non-fatal myocardial infarction and non-fatal stroke.

** Venous thromboembolic events (VTE) include deep vein thrombosis (DVT) and pulmonary embolism (PE).

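### The normal-approximation 95% CI for long-term AESI rates (SAP 10.2.2.1, Appendix B) breaks down at low event counts and understates the upper limit

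*SAP*

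**What the plan says.** SAP 10.2.2 reports long-term adverse events as exposure-adjusted event rates (EAER) in everyone who received upadacitinib 15 mg QD: "The EAER will be the main approach to evaluate AEs in the long-term analysis". A subject may contribute more than one event.

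In the overview (SAP 10.2.2.1), for treatment-emergent AESIs, "the point estimate and 95% CI (using normal approximation) will be provided for the Any Upadacitinib 15 mg QD group". Appendix B supplies the method. It starts from a Poisson model, "Assume the occurrence of TEAE of special interest follows a Poisson distribution", and defines exposure as follows: "Let T be the total number of days exposed to study drug summed across all treated subjects". It then states "Using normal approximation, the 95% confidence interval can be calculated by" the estimate n/T plus or minus the normal quantile times √(n/T²). It gives no rule for zero or few events, no truncation at zero and no alternative interval.

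SAP 10.2.2.3 carries the rate, by reference back to 10.2.2.1, to the individual categories: it "will be calculated overall, for each SOC and each PT, for each of the AESI listed in Section 10.2.1.6". The list in 10.2.1.6 (Table 9) has narrow categories, among them lymphoma, active tuberculosis, MACE, venous thromboembolism and "Adjudicated Gastrointestinal Perforations".

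SAP 10.2.2 also plans a first-event rate: "the exposure-adjusted incidence rate (censored at first event) will be conducted for AESI endpoints as deemed appropriate". No interval method is given for it.

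**The concern.** The standard error in Appendix B is √n/T, so it is estimated from the observed count alone. When that count is zero, the interval has no width and reads as certainty that the rate is zero. When it is small, the interval is symmetric around a quantity that cannot be negative and whose distribution is strongly skewed.

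For a rare AESI the upper limit is what a reader needs, because it says how high a rate the data still allow. The formula errs downwards there, which is the reassuring direction. Long-term safety is a stated Period 2 objective, and only about 170 subjects contribute exposure, so low counts in the narrow categories are foreseeable.

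**Working it through.** **Inputs.** Interval formula and Poisson assumption: SAP Appendix B. Exposure: SAP 4.2, with 85 subjects on upadacitinib for up to 104 weeks (728 days) and 85 switched from placebo at Week 14 and treated for up to 90 weeks (630 days). The plan states no interval to reproduce, and the documents give neither AESI counts for this study nor realised exposure, so a range of counts is shown.

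**Maximum exposure to Week 104, no dropout.** 85 × 728 + 85 × 630 = 61,880 + 53,550 = 115,430 days; 115,430 / 365.25 = 316 patient-years (PY). Exposure only rescales both sets of limits, so the comparison between them does not depend on it.

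**Formulas.**
- Appendix B: (n ± 1.96√n)/T.
- Exact Poisson (Garwood): lower = χ²(0.025; 2n)/(2T), taken as 0 when n = 0; upper = χ²(0.975; 2n+2)/(2T).

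The Appendix B lower limit is negative when 0 < n < 1.96² = 3.84, that is for n = 1, 2 or 3. Example, n = 3: 100 × (3 − 1.96 × 1.732)/316 = −0.12 per 100 PY.

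**Limits per 100 PY at 316 PY.**

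| Events | Appendix B | Exact Poisson | Appendix B upper limit below exact by |
|---|---|---|---|
| 0 | 0 to 0 | 0 to 1.17 | reported as 0 |
| 1 | −0.30 to 0.94 | 0.01 to 1.76 | 47% |
| 2 | −0.24 to 1.51 | 0.08 to 2.29 | 34% |
| 3 | −0.12 to 2.02 | 0.20 to 2.77 | 27% |
| 5 | 0.20 to 2.97 | 0.51 to 3.69 | 20% |
| 10 | 1.20 to 5.13 | 1.52 to 5.82 | 12% |

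If exposure to Week 104 were 200 to 316 PY (an assumed range to allow for dropout), the exact zero-event upper limit would be 1.84 to 1.17 per 100 PY.

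**Coverage.** Poisson probabilities were summed over the counts whose interval contains the true rate. With 0.5 events expected, the probability of none is e^(−0.5) = 0.607; each such result gives 0 to 0 and misses, so coverage cannot exceed 39.3%. With 3 expected, counts of 0 and 1 both give an upper limit below 3 (0 and 2.96), and together they have probability 0.199.

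| Expected events | Appendix B coverage | Upper limit below true rate | Exact coverage |
|---|---|---|---|
| 0.5 | 39.3% | 60.7% | 98.6% |
| 1 | 63.2% | 36.8% | 98.1% |
| 2 | 86.4% | 13.5% | 98.3% |
| 3 | 79.7% | 19.9% | 98.8% |
| 4 | 90.6% | 9.2% | 96.0% |
| 5 | 87.0% | 12.5% | 98.0% |
| 10 | 92.6% | 6.7% | 97.5% |
| 20 | 94.8% | 3.9% | 95.7% |

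Across 0.5 to 5 expected events in steps of 0.01, Appendix B coverage peaks at 94.7% (at 4.77) and never reaches 95%. Exact coverage over the same range is 95.9% to 99.6%.

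**Do such counts occur?** Protocol 3.2 reports no gastrointestinal perforations in two 12-week RA studies (N = 575). The placebo figure there, 2 subjects = 1.9%, implies 103 to 108 placebo subjects and so 467 to 472 on upadacitinib, at most 107 to 109 PY (subjects × 84/365.25). Appendix B would report 0 to 0 for that category; the exact upper limit is about 3.4 per 100 PY. Disease and dose differ, so this is indicative only.

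**First-event rate.** In 40,000 simulated trials (170 subjects followed 728 or 630 days, constant hazard), exact limits covered 96.4% to 98.9% at 0.5 to 20 expected events. The normal approximation covered 40% at 0.5 expected events, 63% at 1 and 87% at 5.

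**The case against.** The algebra is not in dispute; the scope and weight are. The sentence promising an interval sits in the overview, where AESIs form one row among seven. SAP 10.2.2.3 points back to 10.2.2.1 for the rate, but 10.2.2.2 does the same for event classes that have no interval in 10.2.2.1, so the cross-reference may import only the rate. If the interval is for all AESIs pooled, the count is larger. At an assumed 20 to 40 events the upper limit is only 7% to 4% below exact, with coverage of about 93% to 95%. This stands as a real ambiguity. A per-category interval is the more natural reading, but it is not written, and exact limits do no harm under either reading.

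The intervals are single-arm and descriptive. Counts and exposure are printed beside each rate, and serious events, deaths and events leading to discontinuation are listed. A careful reader would notice 0 to 0 and could compute the bound. That limits the consequence, but it does not make the interval a 95% interval.

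The SAP version history says that version 3.0 adds an incidence rate for all AESIs at future locks. That helps with repeat events, but no interval method is attached to it.

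Finally, exact limits on event counts also assume Poisson variation. If subjects have repeat events, even these may be too narrow. This stands, and it is a reason to rely on the first-event rate in that case. It is no argument for the normal approximation, which rests on the same assumption.

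**Conclusion.** The concern holds. As written, Appendix B gives 0 to 0 with no events, an impossible negative lower limit with one to three events, and an upper limit 47% to 12% too low at 1 to 10 events. These results follow from the formula and do not depend on exposure. The figures per 100 PY rest on full exposure to Week 104; dropout lowers that exposure, and the extension in five countries raises it at the final lock. The coverage figures rest on the SAP's own Poisson assumption. Commoner categories are little affected.

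No test, alpha level or efficacy result is touched. It should be fixed, at the lower end of that priority, because the EAER is the main long-term safety measure and the error understates how high a rare risk could be.

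**What to change.** For the Week 104 and final locks:

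1. In Appendix B, replace the normal-approximation limits with the exact Poisson limits given above, with the lower limit set to 0 when n = 0.
2. Use the same limits for the first-event incidence rate if an interval is shown for it, and rely on that rate where subjects have repeat events. A robust Wald variance is not a substitute at low counts, because it is also zero when n = 0.
3. State whether the interval is given for each AESI category or only for AESIs overall.
4. As a minor clarification, check the EAER formula printed in SAP 10.2.2 against the source file, since the text may have been garbled in reading. Then write the rate as 100 × n/(T in days/365.25), and scale the Appendix B estimate and limits, which are per day, by 100 × 365.25 = 36,525.

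The cost is SAP wording and a standard software option. Intervals at low counts become wider and somewhat conservative (coverage up to 99.6%). A table footnote should say that the method differs from the Week 64 lock of February 2020. Nothing is asked for Period 1, whose Week 14 lock is complete.
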